**f. Sample size calculation**

The information reported in the article by Rahat et al., which had a double-blind randomized crossover design, was used to calculate the sample size (13). In this study, a significant

increase in the active PYY response was found when consuming 24 g of inulin mixed with 75 g of glucose dissolved in water (increase in the area under the curve from 0 to 4 h (iAUC04) = 5.69 pmol×h/L ± 9.8 pmol×h/L), compared with consumption of only 75 g of glucose dissolved in water ((iAUC04) = 1.06 pmol×h/L ± 10 pmol×h/L) with a p=0.003.

The program G\*Power v.3.1.9.7 (36) was used for the sample size calculation, and an n=24 was obtained using the formula for dependent mean difference and considering a loss of 25% (which is common in this type of study); 30 subjects would be required for this project.

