Therefore, more scientific evidence is needed to contribute to nutritional recommendations for hunger control and satiety. Therefore, this study aims to evaluate the chemical and sensory characteristics of a coffee and agave inulin-based beverage and its effect on appetite, dietary intake, and biochemical profile in subjects with obesity. For this purpose, a randomized crossover clinical trial with an estimated n of 30 participants has been proposed to evaluate the effect of daily and two-week consumption of a coffee beverage with agave inulin in comparison with the daily and two-week consumption of a placebo beverage for two weeks (Sedes: Instituto de Nutrigenética y Nutrigenómica Traslacional (INNUGET) of the CUCS and the Bariatric and Metabolic Surgery Unit of the Civil Hospital "Juan I. Menchaca"). The measurement of appetite hormones (acetylated ghrelin, GLP-1, and PYY) will be measured by ELISA assays. Visual analog scales measure appetite sensations, and the biochemical profile is determined by dry chemistry. The study will be conducted from April 2024 to March 2025. The results of this research will be disseminated at international

congresses in a high-impact international journal, and its completion will allow several students to complete doctoral and bachelor's theses.

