**e. Exclusion criteria**

Incomplete data and/or measurements

Lack of expected compliance (drink at least 5 of the 7 days of each week is considered compliance).

Individuals who decide to leave the study

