#### Statistical analysis

Quantitative variables will be expressed as mean  $\pm$  standard deviation or median and interquartile range for descriptive statistics, and qualitative variables as frequency or percentage. The normality of the variables is evaluated with the Shapiro-Wilk test. The general linear mixed model will be used to compare the two treatments. The data will be emptied into an Excel spreadsheet to be later imported into the SPSS v.21 program for analysis, considering a value of  $p < 0.05$  as statistically significant. The graphs will be made with Graphpad software version 9.3.1.

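### Sample size: 24 evaluable with a 25% loss needs 32 enrolled; the stated 30 covers only a 20% loss (minor arithmetic error)

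*Protocol*

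**What the plan says.** Section f (Sample size calculation) takes PYY response data from a published crossover study and reports that "an n=24 was obtained using the formula for dependent mean difference". It then moves to the enrolment target by "considering a loss of 25% (which is common in this type of study); 30 subjects would be required for this project". The Abstract repeats the target: "a randomized crossover clinical trial with an estimated n of 30 participants has been proposed".

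Section e (Exclusion criteria) lists "Incomplete data and/or measurements", failure to meet the compliance threshold, and "Individuals who decide to leave the study". The Protocol does not mention replacing participants who are lost. On the analysis, the Statistical analysis section says that "The general linear mixed model will be used to compare the two treatments".

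**The concern.** The three figures 24, 25% and 30 should be linked by one step, and under the usual meaning of a loss rate they are not. If a quarter of those enrolled are lost, 30 participants do not leave the 24 that the Protocol itself calculated.

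The shortfall would fall on the analysed number. Section e removes leavers, non-compliers and anyone with incomplete data, and no replacement is described. A mixed model can use partial data only from participants who stay in the data set, so as section e is written it would not make up the difference. What is at stake is a small loss of power against whatever target was set, and a justification for the enrolment number that does not hold on its own terms.

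**Working it through.** **Inputs**, all from section f of the Protocol: required number 24; loss 25%; enrolment 30. For the conditional power check: means 5.69 and 1.06 pmol×h/L, SDs 9.8 and 10 pmol×h/L. The 0.05 level is in the Statistical analysis section.

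**1. The Protocol's figure.** 24 × (1 + 0.25) = 30. This reproduces the stated 30 exactly. The Protocol does not print the step, so the route is inferred.

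**2. Enrolment that leaves 24 after a 25% loss.** N = n / (1 − loss) = 24 / 0.75 = 32. Check: 32 × 0.75 = 24.

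**3. What 30 delivers at a 25% loss.** 30 × 0.75 = 22.5, that is 22 or 23 evaluable.

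**4. The loss that 30 can absorb.** 1 − 24/30 = 6/30 = 20%.

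**5. Effect on power.** Section f states no target power, sidedness or within-subject correlation, so this step is conditional. Assume a paired t-test, two-sided 0.05, noncentral t. For each assumed target, find the standardised paired difference (dz) that gives that power at 24, then evaluate it at 22 and 23.

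| Assumed target at n = 24 | dz | Power at 23 | Power at 22 |
|---|---|---|---|
| 80% | 0.597 | 78.1% | 76.1% |
| 90% | 0.691 | 88.6% | 87.1% |

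**6. Context for the 24.** The difference is 5.69 − 1.06 = 4.63. The SD of the paired difference is √(9.8² + 10² − 2 × r × 9.8 × 10), where r is the correlation between a participant's two responses. At r = 0.70 this is 7.67, so dz = 4.63 / 7.67 = 0.604, which requires 24 for 80% power. Other values of r at 80% power:

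| r | 0.60 | 0.65 | 0.70 | 0.72 | 0.75 |
|---|---|---|---|---|---|
| Required n | 31 | 28 | 24 | 23 | 20 |

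A required number of exactly 24 arises for r of about 0.694 to 0.707 at 80% power, or about 0.772 to 0.781 at 90%. A shift of 0.05 in r moves the requirement by about 4, which is more than the gap of 2 at issue here.

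**The case against.** The strongest reply is that section f does not say what the 25% is a share of. Read as a 25% addition to the required number, the three figures agree exactly, because 24 × 1.25 = 30. That explains where 30 came from, but it does not fit the text. The Protocol calls the 25% a loss and describes it as usual for studies of this kind, which is the language of an attrition rate among those who start. If an addition to completers was meant, the attrition actually covered is 20% and the sentence still misdescribes it.

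A second reply is that the gap is trivial beside the uncertainty in 24 itself. This stands as a comment on size: step 6 shows that the unstated correlation matters at least as much. It does not make the loss step correct.

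A third is that the analysis set and the handling of missing data may be defined in a statistical analysis plan that is not shown. That is fair. The statement that lost participants reduce the analysed number rests on section e and on the absence of any replacement rule in the Protocol. The arithmetic in steps 1 to 4 does not depend on it.

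Finally, lowering the expected loss to 20% merely to fit 30 would be no correction, since the Protocol offers no evidence for 20%. That also stands, so the corrected sentence should keep the result at 25% in view.

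**Conclusion.** The concern holds. With loss taken as a share of those enrolled, the stated enrolment is 2 short (30 against 32), or 1 to 2 short in evaluable participants (22 to 23 against 24). Thirty enrolled protects 24 only up to a 20% loss.

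The consequence is minor. Under a two-sided 0.05 paired test, power falls by about 2 to 4 percentage points if 24 was set for 80%, and by about 1 to 3 if it was set for 90%. Those power figures rest on assumed targets; the enrolment arithmetic does not. The finding concerns the loss step only and does not show that the trial is inadequately sized.

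**What to change.** Keep 30 and correct the sentence in section f. It should say that 30 enrolled yields 24 evaluable if 20% are lost and 22 to 23 if 25% are lost, and it should give the power at 22 to 23 under the target power, sidedness and correlation that were entered in G*Power. This costs one sentence. The Abstract is unchanged and no extra recruitment is needed for the statement to be correct. The price is openness about the number expected at a 25% loss.

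Alternatively, if the sponsor wishes to keep both the 25% allowance and 24 evaluable, change 30 to 32 in section f and in the Abstract, at the cost of 2 more participants.

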#### **g. Dependent and independent variables**

##### *Independent variable*

Consumption of coffee and agave inulin-based beverage

##### *Dependent variables*

Appetite hormones

Subjective appetite sensations

Dietary intake

Biochemical profile

##### *Confounding variables*

Sex

Age

Habitual coffee consumption

Self-perceived stress

Score in the "Food restriction" section of the three-factor eating questionnaire (TFEQ)

#### **h. Ethical considerations**

This protocol adheres to the ethical principles of the General Health Law on Health Research regulations. According to Article 17 of this law, it is classified as "with higher than minimal risk" since it uses a method of assignment to therapeutic schemes. Likewise, each participant will be given an informed consent form based on the requirements of Article 22 (37).

On the other hand, the Good Clinical Practice (GCP) standards, issued by the International Conference on Harmonization (ICH), will be considered, which detail guidelines for the design, conduct, performance, monitoring, auditing, recording, analysis, and reporting of clinical trials, to ensure that the data and results obtained are accurate and credible and that the rights, integrity, and confidentiality of the study subjects are protected (38).

In addition to the above, the international ethical guidelines for health-related research on human subjects elaborated by the Council for International Organizations of Medical Sciences (39) will be considered, in particular, guideline 5 (choice of control mechanism in clinical trials), guidelines 9 and 10 (on informed consent), guideline 11 (collection, storage and use of biological materials and related data), guideline 12 (collection, storage and use of data), guideline 20 (in disease outbreak situations (for the context of COVID-19)) and guideline 22 (use of online data and digital tools).

### **i. Biosafety Considerations**

#### Instituto de Nutrigenética y Nutrigenómica Traslacional

This institute has a laboratory safety regulation that requires the use of protective clothing such as lab coats, mouth masks, gloves according to the technique to be performed, appropriate footwear, and safety glasses. In addition, all students working on this project will receive a laboratory safety course in which the previously mentioned information is presented, training in good laboratory practices, and their practice will be constantly supervised and advised by trained personnel from the institute. INNUGET has a specific area for storing biohazardous and infectious waste, a specific area for storing reagents, a shower, separate areas for different types of techniques, emergency telephones, evacuation route signs, and a route for transporting biohazardous and infectious waste.

Laboratory techniques to be performed at INNUGET include handling blood, serum, plasma, and genomic DNA extraction (the latter for future use). Blood is collected in vacutainer tubes, and serum, plasma, and genomic DNA are packaged in 1.5 ml Eppendorf tubes at 80% of their capacity and stored at -80°C. Vacutainer tubes containing traces of liquid blood, as well as Eppendorf tubes containing serum, plasma, or genomic DNA that will not be stored, are disposed of in hermetically sealed red containers that comply with the characteristics specified in NOM 087-SEMARNAT-SSA1-2002 (40), temporarily in the area designated for this purpose within INNUGET.

Sharps will be deposited in a rigid red polypropylene container with a lid. Disposable materials used to transfer, contain, inoculate, and mix biological waste will be deposited in red plastic bags. Finally, disposable gloves will be disposed of in the regular trash if not soaked with blood. All this is done according to the specifications of the aforementioned official standard (40). Once the red containers and bags are filled to 80% of their capacity, they are taken to the appropriate containers at the CUCS where a company collects them for incineration.

Likewise, the handling and disposal of chemical reagents with CRETI characteristics will follow the stipulations of NOM-052-SEMARNAT-2005 (41) and their corresponding safety data sheets. It is worth mentioning that before each investigator and student uses the chemical reagents, he/she should carefully read the manufacturers' instructions and make a flow chart of the entire procedure for their use, recorded in the laboratory logs.

Personal protective equipment should be worn in any contingency, and precautionary signs should be followed. The institution's civil protection personnel will be called and asked for help if a spill occurs. They are trained to apply the cleaning and evacuation protocol (if required) based on the nature of the residue or spill. The contact information for this unit is as follows: Unidad Interna de Protección Civil CUCS, Edificio E, [contact]. [name], e-mail [[contact]](mailto:[contact]).

Unidad de Cirugía Bariátrica y Metabólica (Hospital Civil de Guadalajara "[name]"

No chemical reagents will be used at this site. Blood samples will be taken from participants in vacutainer tubes, which will be transferred to INNUGET in a cooler for biological samples for handling and disposal as mentioned in the section of the institute. The sharps used for sample collection will be deposited in a rigid red polypropylene container with a lid, in the area where the sample was collected, in accordance with the specifications of NOM-087-SEMARNAT-SSA1-2002 (40).

[figure not shown]
The protocol has also been submitted to the Ethics Committee of the Civil Hospital "Juan I. Menchaca" (0602-23 HCJIM-2023).

## **METHODOLOGY**

### **Study group**

All participants will be assigned to two interventions separately, according to the random assignment sequence corresponding to the crossover design.

The interventions consist of consuming a beverage (intervention or control) 30 minutes before breakfast daily for 2 weeks, with an intermediate washout period of 2 weeks between each treatment, as shown in Figure 1. Participants will be assigned randomly to the sequence AB (intervention beverage/control) or BA (control/intervention beverage) by generating a table of random numbers in the SPSS software.

*Figure 1. Scheme of the crossover study design*

### **Intervention procedure**

Subjects who attend the Bariatric and Metabolic Surgery Unit of the Nuevo Hospital Civil de Guadalajara “[name]” and who meet the selection criteria. Subjects attend six sessions, one each week. The times and procedures can be seen in the following figure:

[figure not shown]

Figure 2. Intervention study procedure

## Appetite assessment

### Appetite hormones

The hormones and peptides ghrelin are measured in their acetylated form (Biovendor brand kit, catalog #: RA194062400R), GLP-1 (Biovendor brand kit, catalog #: YK160), and PYY (Biovendor brand kit, catalog #: YK080 ), by an ELISA assay and using a Thermo Scientific brand Multiskan Sky spectrophotometer.

### Subjective sensations of appetite

The subjective sensations of appetite consist of 9 questions that are asked in the fasting state and after drinking the beverage. Specifically, 30 minutes before drinking the beverage, immediately after consuming it, 30 and 60 minutes after consumption. These scales assess hunger, fullness, satiety, desire to eat, prospective consumption, and the desire for sweet, salty, fatty, and savory foods. Visual analogue scales are made up of lines, usually 100 mm long, with the term “None” or “Not at all” at one end and “Yes, very much” at the other end. or "As much as I have never felt." The subject marks a point between these two extremes, and the quantification is done by measuring the distance from the left end of the line to the mark to which a score is given (49).

### Sensory specific satiety (SSE)

SSE will be evaluated by visual analog scales of liking and wanting of 100 mm each. The subjective taste or liking of certain sensory characteristics of the food before and after consumption is asked; it is complemented by the evaluation of desire, which is a motivational aspect of appetite or the inclination to consume a specific food (15).

#### Specific sensory desire (SSD)

Fasting, post-beverage, and post-food test participants will be instructed to rate their desire to eat something sweet, salty, sour, bitter, fatty, and spicy using visual analog scales.

#### Food testing

It consists of serving 9 samples of foods with certain sensory properties:

1. Sweet: peach in syrup (13 g)
2. Sour: green apple (8 g) with lemon drops (4 drops)
3. Salty: salted biscuit (4 g)
4. Bitter: cocoa nibs (3 pieces)
5. Spicy: chilled peanuts (3 g)
6. Fatty: avocado (11 g)
7. Ultra-processed sweet: sandwich-type chocolate cookie with flavored filling vanilla (10g)
8. Ultra-processed salty: cheese-flavored corn chips (4 g)
9. Test beverage: it will be the intervention beverage or the control beverage, depending on the phase in which each participant is (20 ml)

Participants will evaluate these foods using scales for sensory-specific satiety and sensory-specific craving. Finally, they will be asked to choose the 3 test foods they would eat the most and the one they would eat the least at that time (15,16).

#### **Dietary intake**

##### Dietary record

In session 1, participants will receive instructions to complete the dietary record form to evaluate their diets. They are asked to record all food and beverages consumed 3 days: a weekday, a weekend day, and the day before the session. This is done in each of the six

sessions. The Nutritionist Pro™ Diet Analysis software (Axxya Systems, Stafford, TX, USA) will be used for analysis.

## **Biochemical profile**

### Blood sample collection

Of the 6 sessions that the participants attend, two blood samples will be taken at the beginning and end of each phase, that is, in 4 sessions.

The first is in the morning, after 8 to 12 hours of fasting by venipuncture, and later 30 minutes after ingestion of the beverage. Two red and one purple vacutainer tubes are obtained, each with 5 ml of blood, centrifuged at 3500 rpm for 15 minutes at 4°C to separate the serum and plasma.

The serum will be used for glucose and lipid profile determinations, the plasma will be used for determining appetite hormones,

### Glucose and lipid profile determinations

The determinations are carried out on the VITROS® 350 automated dry chemistry analyzer equipment. 10 µl of biological sample (serum) is used, which is applied to a slide that contains the reagents that allow the detection of the analyte. These measurements are carried out while fasting and later 30 minutes after ingestion of the beverage.

In addition, capillary glucose measurements will be made with a glucometer (Accu-Check® Roche) while fasting and 30 minutes after ingestion of the beverage. The measurement is done through a puncture with a new, sterile lancet, which obtains a drop of blood that is applied to the reactive area of a strip (Accu-Check® Roche) to be read on the glucometer.

## **Body composition and blood pressure**

Height measurement is done with a Seca stadiometer which has a precision of 0.1 cm. The subject remains standing with feet together (heels together and toes slightly apart). The heels, glutes, upper back, and occipital are in contact with the stadiometer. The head is placed in the Frankfort plane.

### Waist and hip circumference

Waist circumference measurement is performed with a Lufkin brand anthropometric tape, which has an accuracy of 1 mm. The subject keeps his arms crossed on his chest, heels

together with the toes slightly apart, and eyes in the Frankfort plane. The measurement is made at the narrowest level, between the edge of the lower costal rib (tenth rib) and the iliac crest. The subject breathes normally, and the measurement is taken at the end of an exhalation. For waist measurement, the circumference is taken at the maximum posterior level of the gluteal bulge.

#### Electrical bioimpedance

Measurements of fat mass, fat percentage, fat-free mass, and bone mass are obtained through the InBody 370 equipment, under the same conditions described for measuring body weight.

#### Blood pressure

Blood pressure measurement is performed in the morning, after 10 minutes of rest, with a LifeSource digital sphygmomanometer. The patient must be relaxed, sitting, not stretched out, with the back well supported on the back of the chair. His legs should be touching the floor, not crossed, and his hand should be relaxed, without squeezing, and in a resting position. The measurement is carried out on the reference or dominant arm supported more or less at the height of the heart. The subject's clothing does not cover the arm or fit tightly to it.

### **Questionnaires**

#### Medical history

A clinical history will be applied in the first session to obtain information on pathological history, clinical data, nutritional aspects, sociodemographic aspects, and lifestyle.

#### Physical Activity Questionnaire (IPAQ) short version

This instrument is a physical activity evaluation format; it examines different dimensions of the patient's physical activity. Weekly physical activity is measured by recording METs per minute per week. Subjects are classified into 3 categories of physical activity: high, moderate, and low (50). This questionnaire will be applied in the second and third sessions.

#### The Three-Factor Eating Questionnaire

This questionnaire consists of 51 items, is applied in the first session, and evaluates three dimensions of eating behavior: food restriction, disinhibition, and susceptibility to hunger (51). This questionnaire is included in the clinical history.

#### Obtaining a stool sample

At the beginning and the end of each intervention, participants will be asked to provide a stool sample (according to NOM-087-SEMARNAT-SSA1-2002, they are not considered an RBPI). They will be given a kit (sterile collection cup with buffer, collection strip, gloves, and stirrer) and written instructions for the collection procedure. Once subjects submit the sample, aliquots are made into Eppendorf tubes and stored at -80°C for later use.

#### Statistical analysis

Quantitative variables will be expressed as mean  $\pm$  standard deviation or median and interquartile range for descriptive statistics, and qualitative variables as frequency or percentage. The normality of the variables is evaluated with the Shapiro-Wilk test. The general linear mixed model will be used to compare the two treatments. The data will be emptied into an Excel spreadsheet to be later imported into the SPSS v.21 program for analysis, considering a value of  $p < 0.05$  as statistically significant. The graphs will be made with Graphpad software version 9.3.1.

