### **d. Inclusion and non-inclusion criteria**

*Inclusion criteria*

Men and women

25 to 55 years of age

BMI  $\geq$  30 and  $<$ 35 kg/m^2

Habitual coffee consumption (1 - 3 cups of 240 ml daily).

Willingness to stop consuming food and/or supplements with coffee, caffeine, and/or inulin during the study except for the intervention.

Availability of time in the mornings

Residents of the Guadalajara Metropolitan Area

Signed informed consent form

*Non-inclusion criteria*

Hypersensitivity or intolerance to coffee or inulin

Allergy or intolerance to any of the test foods

Current or within the last 6 months use of weight-loss or appetite-altering medications  
appetite altering medications

Diagnosis of diabetes, hypertension or any heart disease, thyroid disease, infectious disease (COVID-19, flu, etc.), digestive or inflammatory bowel disease or dysgeusia

Smoking

Women who are pregnant, want to become pregnant or are breast-feeding

Peri-menopausal or menopausal women

Who is on any dietary regimen for weight loss

Currently or within the last 12 months, participated in another study

Consumption of prebiotics or probiotics in the last three months

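### Does the crossover analysis go wrong because the protocol names neither a period term in the mixed model nor a balance rule for the AB/BA list?

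*Protocol*

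**What the plan says.** Under Statistical analysis the comparison is one sentence: "The general linear mixed model will be used to compare the two treatments". No fixed or random effects are listed and none are ruled out.

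Under Study group, participants go to AB or BA "by generating a table of random numbers in the SPSS software". No block size or ratio appears in the text. People can be dropped after allocation, for example for "Incomplete data and/or measurements" (Exclusion criteria).

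Under Blood sample collection, "two blood samples will be taken at the beginning and end of each phase, that is, in 4 sessions", so phase-start values will exist for the blood measures.

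The list headed Confounding variables holds sex, age, "Habitual coffee consumption", "Self-perceived stress" and the food-restriction score of the Three-Factor Eating Questionnaire. That questionnaire "is applied in the first session, and evaluates three dimensions of eating behavior". The protocol does not say that any of the five enters the model.

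**The concern.** In a two-period crossover, period is the usual nuisance factor, and here a shift between periods is plausible. Entrants are daily coffee drinkers who must show "Willingness to stop consuming food and/or supplements with coffee, caffeine, and/or inulin during the study except for the intervention". On the readable text, phase 1 would follow usual intake and phase 2 would follow a two-week washout. No run-in is described, although the figure that holds the timing is not shown.

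If period is not modelled and the sequences end up uneven, part of that shift is read as a treatment effect. An unrestricted list and later exclusions both make uneven sequences likely. The confounder list also seems to suit a parallel-group trial: four of its five entries have one value per person, so as main effects they cancel within a person, while period is absent. In a trial planned on 24 evaluable people, bias or lost precision could matter.

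**Working it through.** **Inputs.** From Sample size calculation: n = 24, raised to 30; means 5.69 and 1.06, a difference of 4.63; SDs 9.8 and 10. Power and the within-person correlation are not given. Assumed: two-sided 0.05, 80% power (90% as a variant), and a period shift of 0.25 or 0.5 SD of the paired difference.

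**The planned n.** Solving the paired t-test (noncentral t, 23 df) for n = 24 and a difference of 4.63 gives a standardised effect of 0.597 at 80% power. The SD of the difference is then 4.63/0.597 = 7.75 and the implied correlation 0.69. At 90% power the values are 0.691, 6.70 and 0.77. So 24 is attainable, but it can be neither confirmed nor refuted. Results below are in SD units, because the planning outcome is a 0–4 h incremental area, while the readable schedule draws blood only fasting and 30 minutes after the drink.

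**Leak if period is omitted.** With complete pairs,

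E[mean(A − B)] = treatment effect + shift × (nBA − nAB)/N.

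The leaked share is 0 at 12/12, 4/24 = 17% at 14/10, 6/24 = 25% at 15/9 and 8/24 = 33% at 16/8. At 15/9 a shift of 0.25 SD gives a bias of 0.25 × 0.25 = 0.0625 SD, and 0.5 SD gives 0.125 SD. Against 0.597 these are 10% and 21% of the planned effect, in either direction.

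**How uneven.** Binomial(24, 0.5): P(15/9 or worse) = 0.31 and P(14/10 or closer) = 0.69; the mean leaked share is 16%. From a 15/15 list with six losses at random (hypergeometric), P(15/9 or worse) = 0.017.

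**Consequences at n = 24, 80% planned power** (200,000 simulated trials per cell where period is omitted; noncentral t where it is modelled):

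| Situation | Shift 0.25 SD | Shift 0.5 SD |
|---|---|---|
| Period omitted, 15/9, adverse direction: power | 0.69 | 0.51 |
| Period omitted, 9/15, same shift: power | 0.86 | 0.88 |
| Period omitted, 15/9: type I error | 0.054 | 0.060 |
| Period omitted, 12/12: power | 0.78 | 0.72 |
| Period omitted, averaged over simple allocation: power | 0.78 | 0.71 |
| Period omitted, averaged over simple allocation: type I error | 0.05 | 0.05 |
| Period modelled, 15/9: power | 0.77 | 0.77 |

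**Period modelled.** The leak is zero at any split. The variance factor is (N/4)(1/nAB + 1/nBA): 1.00 at 12/12, and 6 × (1/15 + 1/9) = 1.07 at 15/9. Power averaged over simple allocation is 0.78. From a 15/15 list with six random losses it is 0.79, and at exactly 12/12 it is 0.80. Blocking is therefore worth 0.01 to 0.02.

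**Confounders.** Sex, age, habitual coffee and the single questionnaire score take the same value in both phases, so as main effects they drop out of A − B. Entering them would bias nothing. Stress could vary between phases. The readable text gives no session for it, but times and procedures are referred to Figure 2, which is not shown.

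**Phase-start covariate.** The variance factor is about (1 − ρ²)(1 + 1/(N − 4)). At N = 24 this is 1.05, 0.96, 0.79 and 0.54 for assumed ρ of 0, 0.3, 0.5 and 0.7. The range runs from a small loss to a large gain, and nothing in the protocol fixes ρ.

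**The case for a change.** The best case for a change is that not all of this can wait for an analysis plan. The list is drawn before the first participant is randomised, and no later document can restore balance. The one trial that is run keeps its own split, so an average bias of zero is little comfort at 15/9, where power in the adverse direction could fall to 0.51. The confounder list is a choice the protocol does make, and it leaves out the factor that matters most. Naming period costs almost nothing.

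The algebra in this stands, and so does the point about timing of the list. But every large figure depends on period being omitted, which no sentence says. Once period is modelled, imbalance costs only precision, about 0.03 of power at 15/9. Blocks would not remove the problem in any case, because exclusions after randomisation can unbalance a balanced list; the period term is what removes the bias. The 0.51 is also one side of a symmetric picture, since the mirror split gives 0.88. The confounder list is not tied to the model, and its four constant entries do no harm. Whether stress is scheduled cannot be judged without the figure.

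**Conclusion.** No change to the protocol follows. The text leaves detail open; it does not set a rule that gives a wrong result. A mixed model is a suitable class for this design, and its terms (period, sequence, participant, possibly the phase-start value) are what an analysis plan normally supplies. Only the protocol was available here, so their absence from it is not an error. An analyst fitting a two-period crossover would ordinarily include period, and the leak is then zero.

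If period were omitted, the harm would be real but conditional: 25% of the shift at 15/9, with type I error of 0.054 to 0.060 at that split and about 0.05 over allocation. The unblocked list on its own costs 0.01 to 0.02 of power. Using the phase-start value is a choice about precision, with a gain that depends on an unknown correlation.

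The leaked share and the split probabilities follow from n = 24 and simple allocation. The power and type I figures also rest on the assumed 80% power, shifts of 0.25 and 0.5 SD and complete pairs; the comparison with a blocked list assumes losses at random.
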